| ATTACHMENT 3. CRS DERIVATION | 53 | |
| Some examples | 55 | |

AMENDMENT HISTORY

NAP

ABBREVIATIONS

| | |
|---------|---|
| Ab | Antibodies |
| AE | Adverse event |
| ALT | Alanine aminotransferase |
| AST | All subjects treated / Aspartate aminotransferase |
| BIPAP | Bi-level positive airway pressure |
| BMI | Body mass index |
| CI | Confidence interval |
| CPAP | Continuous positive airway pressure |
| CRP | C-Reactive protein |
| CRS | Clinical recovery scale |
| CTP | Clinical trial protocol |
| CU | Confirmed undetectability (of viral loads) |
| DBP | Diastolic blood pressure |
| DMC | Data monitoring committee |
| DMID | Division of Microbiology and Infectious Diseases |
| DPS | Data presentation specifications |
| ECG | Electrocardiogram |
| ECMO | Extracorporeal membrane oxygenation |
| eCRF | Electronic case report form |
| HR | Heart rate |
| IA | Interim analysis |
| ICF | Informed consent form |
| ICH | International conference on harmonization |
| ICU | Intensive care unit |
| IMV | Invasive mechanical ventilator/ventilation |
| IMG | Immunogenicity |
| IQR | Interquartile range |
| ITT | Intent-to-treat |
| IV | Intravenous |
| IWRS | Interactive web response system |
| KM | Kaplan Meier |
| LDH | Lactate dehydrogenase |
| LLN | Lower limit of normal |
| LLOQ | Lower limit of quantification |
| LOQ | Limit of quantification |
| MedDRA | Medical dictionary for regulatory activities |
| NGS | Next generation sequencing |
| NOS | Not otherwise specified |
| NP | Nasopharyngeal |
| PK | Pharmacokinetic(s) |
| PP | Per-protocol |
| PT | Preferred term |
| qRT-PCR | Quantitative real time polymerase chain reaction |
| RAND | Randomized |
| SAE | Serious adverse event |
| SAP | Statistical analysis plan |
| SBP | Systolic blood pressure |

| | |
|---------|----------------------------------|
| SD | Standard deviation |
| SE | Standard error |
| SOC | Standard of care |
| SOC-Med | System organ class as per MedDRA |
| TFL | Tables, figures, and listings |
| ULN | Upper limit of normal |
| ULOQ | Upper limit of quantification |
| VOC | Variant of concern |
| VOI | Variant of interest |

1 INTRODUCTION

This statistical analysis plan (SAP) contains definitions of analysis sets, derived variables and statistical methods for the analysis of efficacy and safety of the investigational compound Sirukumab (**CNTO136COV2001**). A document 'Data Presentation Specifications (DPS)' for mock shells and table of contents for Tables, Figures and Listings (TFLs) is also produced. The SAP is to be interpreted in conjunction with the protocol. The current SAP will cover the primary analysis and the final analysis. Primary analysis will be performed when all randomized participants reach the Day 28 assessment of the study or discontinued earlier. The final analysis will be performed using all data available (including the information from the follow-up visits) after all randomized and/or treated participants reach the end of the study (Week 16) or discontinued earlier. The analysis methods will essentially remain the same for the two analyses.

1.1 Trial Objectives

Primary Objective

The primary objective of the study is to evaluate the clinical response of Sirukumab (administered as a single IV dose) with standard-of-care (SOC) treatment compared to placebo with SOC in confirmed critical COVID-19 disease and as measured by the time to sustained improvement of at least 2 categories relative to baseline on the 6-point ordinal clinical recovery scale (CRS) (up to Day 28).

Secondary Objectives

| Objectives | Endpoints |
|---|---|
| Key Secondary | |
| To evaluate the clinical response of Sirukumab + SOC compared to placebo + SOC in confirmed critical COVID-19 disease | 
 Proportion of participants with an improvement on Day 28 of at least 2 categories relative to Baseline on the 6-point ordinal clinical recovery scale. Incidence of all-cause mortality (up to Day 28) |
| Other Secondary | |
| To evaluate the clinical response of Sirukumab+ SOC compared to placebo + SOC in confirmed severe or critical COVID-19 disease | 
 Time to sustained improvement of at least 2 categories relative to Baseline on the 6-point ordinal clinical recovery scale (up to Day 28) |
| To evaluate the clinical response of Sirukumab + SOC compared to placebo + SOC in confirmed severe or critical COVID-19 disease | 
 Proportion of participants with an improvement on Day 28 of at least 2 categories relative to Baseline on the 6-point ordinal clinical recovery scale Incidence of all-cause mortality (up to Day 28) |
| To evaluate the safety of Sirukumab + SOC compared to placebo + SOC | 
 Incidence of SAEs (up to Day 28) |

| | |
|--|---|
| in confirmed (a) critical and (b) severe or critical COVID-19 disease | 
 Incidence of related AEs (up to Day 28) Proportion of participants with severe or life-threatening bacterial, invasive fungal, viral or opportunistic infections (other than SARS-CoV-2) (up to Day 28) Incidence of grade 3 and 4 neutropenia and lymphocytopenia (up to Day 28) Incidence of increased ALT ≥ 3xULN combined with increased bilirubin > 2xULN (up to Day 28) |
| To evaluate the clinical response of Sirukumab + SOC compared to placebo + SOC in confirmed (a) critical and (b) severe or critical COVID-19 disease | 
 Time to sustained improvement of at least 1 category relative to Baseline on the 6-point ordinal clinical recovery scale (up to Day 28) Proportion of participants with an improvement on Day 28 of at least 1 category relative to Baseline on the 6-point ordinal clinical recovery scale Time from study intervention to end of oxygen supplementation (up to Day 28) Time from study intervention to hospital discharge among the surviving participants (up to Day 28) Total length of hospitalization among the surviving participants (up to Day 28) Number of ventilation free days (up to Day 28) Participant's clinical status at Day 7, 14, 21, 28 (6-point ordinal clinical recovery scale) Total time on invasive mechanical ventilation Proportion of participants with a worse category relative to Baseline on the 6-point ordinal clinical recovery scale (up to Day 28) Proportion of participants on extracorporeal membrane oxygenation (ECMO) over time Total time on ECMO |
| To evaluate the safety during follow-up for (a) critical and (b) severe or critical COVID-19 disease | 
 Proportion of alive participants at Day 28, Week 8, and Week 16 Proportion of alive participants that required readmission at Week 8 and Week 16 (if previously discharged) Incidence of SAEs up to Week 16 |

| Exploratory | |
|--|--|
| To evaluate biomarkers that may be associated with response to or complications of Sirukumab treatment | Evaluations may include, but are not limited to, IL-6, procalcitonin, C-Reactive protein (CRP), ferritin, LDH and D-dimer serum concentrations (through Day 28) |
| To explore changes in SARS-CoV-2 viral load and viral genome | 
 Time to SARS-CoV-2 undetectable viral load by RT-PCR (up to Day 28) SARS-CoV-2 viral load over time by RT-PCR (up to Day 28) Proportions of participants with undetectable viral load (at multiple time points up to Day 28) Development of SARS-CoV-2 variants |
| To evaluate the incidence of SARS-CoV-2 viremia | 
 Proportion of participants with SARS-CoV-2 viremia (as multiple time points up to Day 28) |
| To evaluate pharmacokinetics following Sirukumab 5 mg/kg treatment | 
 Sirukumab serum concentration |
| To evaluate immunogenicity following Sirukumab treatment | 
 Proportion of participants with Sirukumab antibodies (Day 28 or at discharge if discharged after Day 28) |
| To evaluate SARS-CoV-2 humoral immunity | 
 Serum levels of SARS-CoV-2 specific antibodies |

At the time of data analysis, additional endpoints may be considered for analysis in function of the evolution in scientific knowledge on COVID-19.

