3. OBJECTIVES AND ENDPOINTS

Objectives	Endpoints
Primary	
To evaluate the clinical response of sirukumab (administered as a single IV dose) + SOC compared to placebo + SOC in confirmed critical COVID-19 disease	
 • Time to improvement^a of at least 2 categories relative to Baseline on the 6-point ordinal clinical recovery scale (up to Day 28)
Key secondary	
To evaluate the clinical response of sirukumab + SOC compared to placebo + SOC in confirmed critical COVID-19 disease	
 • Proportion of participants with an improvement on Day 28 of at least 2 categories relative to Baseline on the 6-point ordinal clinical recovery scale • Incidence of all-cause mortality (up to Day 28)
Other Secondary	
To evaluate the clinical response of sirukumab (administered as a single IV dose) + SOC compared to placebo + SOC in confirmed severe or critical COVID-19 disease	
 • Time to improvement^a of at least 2 categories relative to Baseline on the 6-point ordinal clinical recovery scale (up to Day 28)
To evaluate the clinical response of sirukumab + SOC compared to placebo + SOC in confirmed severe or critical COVID-19 disease	
 • Proportion of participants with an improvement on Day 28 of at least 2 categories relative to Baseline on the 6-point ordinal clinical recovery scale • Incidence of all-cause mortality (up to Day 28)
To evaluate the safety of sirukumab + SOC compared to placebo + SOC in confirmed (a) critical and (b) severe or critical COVID-19 disease	
 • Incidence of SAEs (up to Day 28) • Incidence of related AEs (up to Day 28) • Proportion of participants with severe or life-threatening bacterial, invasive fungal, viral or opportunistic infections (other than SARS-CoV-2) (up to Day 28) • Incidence of grade 3 and 4 neutropenia and lymphocytopenia (up to Day 28) • Incidence of increased ALT $\geq 3 \times$ULN combined with increased bilirubin $> 2 \times$ULN (up to Day 28)

^aThe improvement should be sustained until Day 28 (or discharge/discontinuation).

Objectives	Endpoints

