5. If a participant is discharged from the hospital, the day of discharge will be considered as “hospitalized”. The participant will be categorized in the category the participant was in at time of discharge. After this day, the participant will be considered “Not hospitalized” until day 28 or trial discontinuation, whichever comes first.

Baseline

The 6-point ordinal CRS at the time of randomization request will be used as the baseline. If the baseline assessment of the CRS is missing, the first available assessment within 12 hours after randomization will be used. If the latter is also missing, the last available assessment prior to baseline will be used.

Sustained Clinical Improvement

Clinical Improvement is obtained if the score on the CRS improved with at least 2 categories with respect to the baseline score.

Sustained clinical improvement is defined as a clinical improvement without documented loss of this clinical improvement up to and including day 28 or until trial discontinuation, whichever comes first.

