5.3 Key Secondary Endpoints

5.3.1 Definitions

Similar as for the primary endpoint, the definitions as specified in section [5.2.1](#) will be used for the key secondary endpoints.

Clinical improvement at Day 28

Clinical Improvement is obtained if the score on the CRS improved with at least 2 categories at Day 28 with respect to the baseline score.

All-cause mortality up to Day 28

All-cause mortality is defined as score 6 on the CRS at Day 28.

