5.3.2 Key Secondary Estimands

Clinical improvement at Day 28

Population: The population of interest are hospitalized patients between ≥ 18 and <85 years old with confirmed critical COVID-19 disease.

Endpoint: Sustained clinical improvement at Day 28 (yes/no)

Interventions: Received Sirukumab 5 mg/kg (IV single dose infusion on Day 1) and placebo (IV infusion on Day 1), both on top of SOC.

Intercurrent Events:

- Death as intercurrent event is handled in a composite strategy as it is the worst category on the clinical scale. Participants that died at Day 28 or earlier will be considered as failure (Sustained clinical improvement at Day 28=no), irrespective of whether a clinical improvement occurred prior to death.
- The intercurrent event of the use of prohibited medication is handled in a treatment policy strategy: data will be used as observed.
- The intercurrent event of discharge to the alternate care settings ‘different hospital’, ‘acute care facility’, ‘subacute care facility’ or ‘hospice/palliative discharge’ is handled in a while on treatment strategy: see section 5.2.1
- Participants that discontinue the study before Day 28 will be considered as failure (Sustained clinical improvement at Day 28=no), unless they had an event of sustained clinical improvement prior to discontinuation. In the latter scenario it will be considered a success (Sustained clinical improvement at day 28=yes).

Population-level summary measure:

The difference in proportion of participants with of ‘Sustained clinical improvement at Day 28’ for experimental treatment versus placebo.

All-cause mortality up to Day 28

Population: The population of interest are hospitalized patients between ≥ 18 and <85 years old with confirmed critical COVID-19 disease.

Endpoint: Death by Day 28 (Yes/No)

Treatment: Sirukumab 5 mg/kg (IV single dose infusion on Day 1) and placebo (IV infusion on Day 1), both on top of SOC.

Intercurrent events:

- The intercurrent event of the use of prohibited medication is handled in a treatment policy strategy: data will be used as observed.
- Participants that discontinue the study before Day 28 with a score > 1 on the CRS will be analyzed according to the composite strategy and will be considered as death on day 28 (Death by day 28=yes).

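### SAP 5.3.2 codes a participant who leaves the study improved but still at CRS 2 or 3 as improved at Day 28 and also as dead by Day 28

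*SAP*

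**What the plan says.** **Endpoint as listed.** SAP 1.1 gives the first key secondary endpoint as "Proportion of participants with an improvement on Day 28 of at least 2 categories relative to Baseline", and Protocol section 3 agrees: "Proportion of participants with an improvement on Day 28 of at least 2 categories relative to Baseline on the 6-point ordinal clinical recovery scale". SAP 5.3.1 defines it as a score that has "improved with at least 2 categories at Day 28 with respect to the baseline score".

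**Endpoint as estimated.** SAP 5.3.2 labels the variable differently: "Endpoint: Sustained clinical improvement at Day 28 (yes/no". SAP 5.2.1 defines sustained improvement as "clinical improvement without documented loss of this clinical improvement up to and including day 28 or until trial discontinuation, whichever comes first", so the requirement can end when the participant leaves the trial.

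**Early discontinuers, improvement.** SAP 5.3.2 makes them failures "unless they had an event of sustained clinical improvement prior to discontinuation. In the latter scenario it will be considered a success". The last CRS score plays no further part.

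**Early discontinuers, mortality.** The same section says: "Participants that discontinue the study before Day 28 with a score > 1 on the CRS will be analyzed according to the composite strategy". It then counts them as dead on Day 28. Those whose last score was 1, with no reported death, count as alive.

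**Missing scores.** Under SAP 5.2.1 the CRS is missing after discontinuation for any reason other than death.

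**Order of testing.** Protocol 9.4 tests the primary endpoint first, then Day 28 improvement, then mortality. Each key secondary is tested at one-sided 5%.

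**The concern.** The two key secondary endpoints describe the same participants at the same time. For one kind of discontinuer they assert Day 28 states that cannot both be true. Neither state is observed: no Day 28 score supports the success, and no date of death supports the score of 6 by which SAP 5.3.1 defines mortality.

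The same person then helps an arm at one step of the hierarchy and counts against it at the next. Reaching an improved inpatient state may itself depend on treatment, so the number coded both ways could differ between arms. No analysis in SAP 5.3.3 varies the discontinuer rule. The sensitivity model there adjusts for covariates, and the pre/post-interim and ITT repeats keep the same coding.

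**Working it through.** **1. The plan's own figure.** SAP 1.4 gives 74 sirukumab and 37 control participants, improvement of 55% vs 30%, mortality of 15% vs 40%, one-sided 5%, and at least 80% power for both. The normal approximation is power = Φ[(Δ − 1.645·se0)/se1]. Here se0 uses the pooled proportion and se1 the separate proportions.

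- Improvement: pooled p = (37×0.30 + 74×0.55)/111 = 0.467; se0 = 0.1005; se1 = 0.0950; (0.25 − 0.1652)/0.0950 = 0.89; power 81.4%.
- Mortality: pooled p = (37×0.40 + 74×0.15)/111 = 0.233; se0 = 0.0852; se1 = 0.0906; (0.25 − 0.1401)/0.0906 = 1.21; power 88.7%.

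The stated power is reproduced. It is not what is at fault.

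**2. The two rules applied to every discontinuer.** SAP 2.2.3 restricts the primary analysis set to baseline CRS 4 or 5. For someone who leaves before Day 28 with no documented loss of any improvement:

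| Baseline | Last CRS | Improvement estimand | Mortality estimand |
|---|---|---|---|
| 4 | 1 | success | alive |
| 4 | 2 | **success** | **dead** |
| 4 | 3, 4 or 5 | failure | dead |
| 5 | 1 | success | alive |
| 5 | 2 | **success** | **dead** |
| 5 | 3 | **success** | **dead** |
| 5 | 4 or 5 | failure | dead |

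Three combinations conflict: 4 to 2, 5 to 2 and 5 to 3.

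**3. Effect per participant.** 1/74 = 1.4 points in the sirukumab arm and 1/37 = 2.7 points in control, on each endpoint.

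**4. Effect on power, over an assumed range.** The documents give no discontinuation rate. Let d be the share of an arm coded both ways, assumed to be 2%, 5% or 10%. For improvement, the design rates are taken as including these participants, and d is subtracted to make them failures. For mortality, d is added to the design death rates.

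| Where d falls | Improvement, from 81.4% | Mortality, from 88.7% |
|---|---|---|
| Both arms equally | 81.8 / 82.7 / 84.9% | 87.5 / 85.8 / 83.5% |
| Sirukumab only | 75.3 / 64.7 / 44.9% | 83.0 / 71.8 / 49.3% |

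Equal shares change little. An imbalance between arms matters, and the second row is its extreme form.

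**5. A constructed borderline case** (unstratified pooled z-test, one-sided):

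- 36/74 vs 12/37: z = 0.1622/0.0997 = 1.63, p = 0.052.
- Two improved leavers counted as sirukumab successes, 38/74 vs 12/37: z = 0.1892/0.1002 = 1.89, p = 0.029.
- The same two plus one in control, 38/74 vs 13/37: z = 0.1622/0.1003 = 1.62, p = 0.053.

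**The case against.** **The rules are prespecified, and separate estimands may treat discontinuation differently.** True. A worst-case imputation for mortality is a recognised choice. What remains is that two adjacent confirmatory steps assume incompatible Day 28 facts about one person.

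**A reader might infer that the composite strategy for death is broken.** The documents do not support that. The failure rule in SAP 5.3.2 covers participants who actually died, and Attachment 3 derives score 6 from the date of death. A discontinuer coded dead for the mortality endpoint is an imputation for that endpoint only.

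**A reader might infer that status at discontinuation counts only for time-to-event endpoints.** That is true of the protocol footnotes. However, SAP 5.4.1 also allows status at discharge or discontinuation for two Day 28 proportions: improvement of at least 1 category, and improvement of at least 2 categories on the as-observed scale. The SAP therefore uses this convention elsewhere. It does not state it in SAP 1.1 or 5.3.1 for the key secondary endpoint.

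**The affected group is narrow.** This stands. Protocol 7.2 allows withdrawal only for loss to follow-up, withdrawn consent or death, and 7.3 ties loss to follow-up to the phone visits. Ordinary discharge gives CRS 1 from the next day, where the two rules agree. What is left is mainly consent withdrawn in hospital at CRS 2 or 3, or dropout after transfer to a setting that SAP 5.2.1 still counts as hospitalised.

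**The present success rule matches the primary.** Also true. SAP 5.2.3 counts sustained improvement before discontinuation as an event, so changing the key secondary gives up that agreement.

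**Conclusion.** The conflict is real and can be read directly from SAP 5.3.2. Early discontinuers in three baseline-to-last-score combinations are counted as improved at Day 28 and as dead by Day 28, with no Day 28 score behind either. The endpoint estimated also differs from the one defined in SAP 1.1 and 5.3.1.

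The only size the documents support is 1.4 or 2.7 points per participant on each endpoint. How many participants are affected is unknown and may be few. It would be tempting to say that the coding decides whether mortality is tested. The shift from 0.052 to 0.029 shows only that two people can matter in a chosen case with both in one arm. One more in control returns p to 0.053, and the primary must succeed first in any case.

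The mortality rule has a further gap. The schedule of activities (Protocol 1.3, footnote n) and Protocol 8.2.6 provide for a Day 28 call that records vital status for early discontinuers who have not withdrawn consent. SAP 5.3.2 makes no exception for someone found alive on that call.

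**What to change.** In SAP 5.3.2, assign each early discontinuer one Day 28 status and use it for both key secondary endpoints.

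- **Vital status at Day 28 known:** use it for mortality, so that a discontinuer known to be alive is not coded dead.
- **Vital status unknown and last CRS above 1:** keep the worst-case death coding for mortality, and count the participant as a failure for Day 28 improvement.
- **Last CRS 1 with no reported death:** no change is needed, because the two rules already agree.
- **Sensitivity analysis:** keep the present rule (success if improved before discontinuation), which matches the primary's event rule.
- **Wording:** say that the primary counts improvement sustained to discontinuation while this endpoint requires Day 28 status, and align SAP 1.1, 5.3.1 and 5.3.2. The SAP should also say how improvement is scored for a discontinuer known to be alive but without a Day 28 CRS. If Day 28 status is required, that participant is alive and not improved, which is at least coherent.

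The cost is SAP wording and one derived flag. The improvement rate may be slightly less favourable, and the endpoint no longer follows the primary's discontinuer rule. Known vital status will not resolve every case, because Protocol 7.3 bars collecting it after consent is withdrawn.

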1.2 Trial Design

This is a randomized, double-blind, placebo-controlled, multicenter, interventional Phase 2 study in hospitalized participants with confirmed COVID-19 disease, at risk for progressing to severe ARDS.

Up to protocol amendment 4, target was to randomly assign 270 participants with confirmed severe or critical COVID-19 in a 2:1 ratio (Sirukumab: placebo) to receive 1 of the following 2 treatments:

- Treatment Arm: Sirukumab 5 mg/kg IV single dose infusion on Day 1 + SOC treatment
- Control Arm: placebo IV single dose infusion on Day 1 + SOC treatment

As of protocol amendment 5 (please also see section 1.4: 'Sample Size Justification' for revised sample size calculations), the study aims to enroll approximately 111 participants with confirmed critical COVID-19 disease overall in the study. The primary and key secondary analyses will be tested on the participants with confirmed critical COVID-19 disease.

At the time of release of protocol amendment 5, approximately 100 participants with confirmed severe COVID-19 disease had been enrolled. The overall population of participants with confirmed severe or critical COVID-19 disease will be analyzed as part of secondary objectives of the study.

Randomization is stratified by age (<65 and \geq 65 years of age) and by use of invasive mechanical ventilation (yes/no) at the time of randomization.

The study will include a ‘Screening Phase’, a ‘Day 1 to Day 28’ Phase (‘Treatment Phase’) and a Post Day 28 ‘Follow-up Phase’ to include phone calls on Week 8, Week 12 and Week 16. The entire study duration for each participant will be 16 weeks with daily study assessments up to Day 28 or day of discharge (whichever comes first), and phone call assessments thereafter, ie, at Day 28 in case of discharge prior to Day 28, at Week 8, 12 and 16. The assessment schedule will be on a weekly basis for participants still hospitalized after Day 28. The study is considered completed with the completion of the last study assessment (phone call assessment at Week 16) for the last participant in the study or the discontinuation of the last participant in the study, whichever comes last.

